8.1.2.4 DIGIHALER™, TEACHING, AND ONLINE APPLICATION

Education for the appropriate use of the Digihaler™ will be provided at the Screening/Baseline visits and again as needed throughout the study. The study team will assist in registering for the digital inhaler application and periodically check to ensure data is being captured appropriately.

Inhalation parameters and number of doses will automatically be collected using the Digihaler™.

Application

The software App is a user facing software/focused smart device application for patients using the Digihaler™ product. The smart device app is used to track medication usage and allow users to self-assess their respiratory symptoms on a daily basis, share information on local environmental conditions, and produce user reports to review data over time.

The software consists of a smart device application compatible for iPhone operating systems (iOS) and Android operating systems that will store data locally on the patient's smart device. The App will receive a patient's health data automatically from the inhaler devices via Bluetooth on a smart device. The smart device camera will be used for scanning and pairing. The data will allow the patient to track their usage of medication, inhalation results, and self-assessments related to their asthma. The App will get environmental information from 1 or more web services.

TEVA Digital Health Platform

The TEVA DHP is a system that stores and transfers health data collected from the App. The cloud solution automatically synchronized with the App after events and/or at predetermined time periods/intervals. An internet connection to the smart device (e.g., wireless or cellular phone network) is required in order for communication to be established between the App and the cloud solution. The

cloud solution will not send any notifications to the App. The cloud solution does not create, modify, or delete patient information.

Patient privacy will be maintained according to the laws and regulations, and patient identifiers will be substituted to maintain a patient's privacy to reviewers of the data.

8.1.2.5 SPIROMETRY

Home spirometry will be performed with the Go Spiro device that is coupled with an avatar that provides coaching and real time feedback about whether the testing has met ATS criteria. Patients will be asked to perform spirometry a *least* three days per week, at least one of which occurs on the weekend. Patients will be asked to make a maximum of three attempts to obtain data. Patients will be encouraged to complete more than three readings per week whenever possible. The spirometry should be obtained at approximately the same time of each day.

The vendor providing central spirometry services will be responsible for assuring that the spirometer used by patients at home meets ATS/ERS criteria and that study staff educating participants on home spirometry have been properly certified to provide this training.

Subjects should be instructed to follow the required restrictions below prior to performing spirometry. If the required restrictions have not been adhered to the visit should be rescheduled to the earliest possible time to maintain the visit windows.

Home Spirometry Testing

An electronic hand-held spirometer will be provided to the subject at the screening visit. Subjects will be trained on how to obtain at home PEF and FEV1 measurements at the screening visit. Training should include explanation of the device functionality and proper use of the PEF meter.

Home PEF measurements will be taken in the morning (prior to taking morning medications) and/or in the evening at bedtime (prior to taking pm medications for asthma) on the days that spirometry is done. FEV1 will be measured at home using accepted ATS/ERS criteria via the use of an avatar guided maneuver. Subjects should perform 3 successive maneuvers while sitting or standing but in the same position at every testing. Adherence to peak flow measurements must be checked by the study coordinator at every in-person visit. A low compliance trigger will be sent to the study site if the subject had completed less than 80% of the expected measurements over a seven-day period.

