2.3.3 ASSESSMENT OF POTENTIAL RISKS AND BENEFITS

This is a minimal risk study that will focus on real world use of approved medications with an emphasis on understanding patterns of use, inhalational parameters, and changes in these measurements during acute episodes of asthma. Patients will be encouraged to follow the clinical guidance that is provided by the treating physician.

The ProAir® Digihaler™ is a rescue/reliever agent that includes an eModule on top of the approved PROAIR® RESPICLICK inhaler. The system consists of the ProAir® Digihaler™, the App, the cloud solution, and the dashboard. The ProAir® Digihaler™ can be used with or without the additional devices (App, cloud solution, and dashboard) that are being evaluated in this study. The on-board electronics and power source in the Digihaler™ are fully integrated into the inhaler and are designed to operate for the life of the inhaler without intervention. The eModule records timestamped pre-defined events. The inclusion of the eModule has been shown to have no impact on the dose delivery compared with the approved product without the eModule (performance and functional testing on file at Teva). Furthermore, the steps to take a dose of ProAir® Digihaler™ are identical to that of the currently approved PROAIR® RESPICLICK. Therefore, it is unlikely that the inclusion of the eModule will add additional risk to the approved product. In summary, the benefit and risk assessment for ProAir® Digihaler™ is favorable following review of the outlined data.

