6.1.2 DOSING AND ADMINISTRATION

Patients will receive the ProAir® Digihaler™ 90mcg and the AirDuo® Digihaler™ at a dose that is equivalent to the patients current inhaled therapy dose. Most patients will likely require the high dose inhaler: 232/14 device. This medication will be administered twice daily. The ProAir® Digihaler™ will be utilized up to six times per day as needed for acute asthma symptoms.

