6.2.2 FORMULATION, APPEARANCE, PACKAGING, AND LABELING

The prescribed dose of ProAir® Digihaler™ used in this study (i.e., 90 mcg, 1 to 2 inhalations every 4 to 6 hours, as needed) was selected based on the prescribing information for PROAIR® RESPICLICK, which has the same drug delivery design as ProAir® Digihaler™. The prescribed dose of AirDuo® Digihaler™ is based on current FDA approval for the AirDuo® inhaler. The inhaler used in this study will have the digital interface for data collection, and this should not impact the drug delivery in any way. The digital inhaler is longer than the conventional inhaler but is otherwise used similarly.

Supplies of IMP will be labeled according to the current International Council for Harmonization (ICH) guidelines on Good Clinical Practice (GCP) and Good Manufacturing Practice and will include any locally required statements.

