9.4.3 ANALYSIS OF THE SECONDARY ENDPOINT(S)

1. To develop an algorithm that can identify probable imminent exacerbation events using Digihaler™ inhalation parameter measurements, we will compare the performance of several different machine learning regression models. Since we expect our training set to be relatively small with a low event rate, we plan to use the entire inhalation parameter dataset for model training but will employ repeated k-fold cross-validation to reduce variance (over-fitting) and include non-linear features to reduce bias (under-fitting). Examples of features that could be computed and included in this model include but are not limited to: difference between current value and patient-specific 7-day moving average, difference between current value and patient-specific 24-hour moving average, 7-day sample entropy, 24-hour sample entropy, difference in Min-Max over last 24 hours, etc.

A logistic regression model would treat the outcome (exacerbation) as a binary (Yes/No) event. The output of this model would be a daily probability between 0 and 1 that an exacerbation event will occur within a certain period of time. Different models will be fit for different periods of time (e.g., 24, 48, 72 hours) and the performance of each model assessed and compared to others. A recurrent event survival model would treat the exacerbations as discrete events in time. The output of this model would be the predicted time (e.g., in decimal days or hours) until the next event. Other models may include convolutional and/or recurrent neural networks (RNN) with LSTM or GRU architecture with varied numbers of hidden layers.

2. To determine whether and how PIF is associated with FEV1 and FVC, we assess the linearity and strength of the relationship using scatter plots, calculate the paired correlations (Pearson, Kendall, and Spearman), and compute univariate linear regression equations with PIF as the predictor and FEV1 or

FVC as the response. If non-linearity is found, we will determine the appropriate PIF transformation or polynomial term to use in the regression. Regression summary statistics (e.g., R-squared, Mean Absolute Error, Coefficients, and p-values) will be reported.

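### Home FEV1 is timed by the clock alone and analysed without regard to as-needed rescue use, so moderate FEV1 changes and the PIF–FEV1 relation can be distorted

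*Combined protocol and SAP*

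**What the plan says.** Section 8.1.2.5 sets these rules for home measurements:

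- All spirometry: "The spirometry should be obtained at approximately the same time of each day".
- PEF: "Home PEF measurements will be taken in the morning (prior to taking morning medications) and/or in the evening at bedtime", with the evening reading also placed before evening asthma medication.
- FEV1: "FEV1 will be measured at home using accepted ATS/ERS criteria via the use of an avatar guided maneuver". This sentence has no medication timing.
- Restrictions: "Subjects should be instructed to follow the required restrictions below prior to performing spirometry". Nothing that follows mentions rescue inhaler or nebuliser use.

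Rescue use is open through the day. Section 6.1.2 states: "The ProAir® Digihaler™ will be utilized up to six times per day as needed for acute asthma symptoms". Section 6.5.1 also allows nebulised bronchodilators for severe symptoms during exacerbations.

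For the analysis, section 9.4.3 item 2 will "calculate the paired correlations (Pearson, Kendall, and Spearman), and compute univariate linear regression equations with PIF as the predictor". The outcomes in these regressions are the two spirometry measures, FVC and FEV1. The item has no flag, covariate or exclusion for rescue use. A 10% FEV1 change appears twice in section 3: in the objective on PIF thresholds, and as one factor in the biologic response categories. FEV1 change up to one year is also a secondary endpoint.

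**The concern.** An FEV1 taken after a bronchodilator is not the same measurement as one taken before it. If the two were mixed in constant proportion, the result would mostly be noise. The protocol gives reason to expect otherwise. Section 2.1 lists increased short-acting beta-agonist use as a risk factor for exacerbations and reports changes in rescue doses around acute events. Section 3 says that the number of inhalations is affected by changes in asthma control. Post-rescue readings may therefore be commoner in the periods when FEV1 is falling. A fixed clock time does not prevent this, because as-needed use varies from day to day at the same hour.

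The pairing adds a second route. A PIF from the rescue inhaler is recorded during the inhalation, before that dose has acted, whereas an FEV1 taken soon afterwards reflects the dose.

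At stake are the PIF–FEV1 correlation and slope, the PIF threshold linked to a 10% lung function change and, if home FEV1 is the source, the FEV1 component of the response categories.

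**Working it through.** **Plan's own figure.** There is none on this point. The documents give no bronchodilator gain, no share of sessions after rescue, and no precision target for FEV1. The stated precision of plus or minus 3 is for mean PIF and is not an input here.

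**Assumed inputs (not in the documents).** A post-rescue reading is higher by a proportion g of 5–12%. The share of sessions taken after rescue rises by d, 20–60 percentage points, in a bad period. The reference share is taken as zero.

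**Averaged over sessions.** With a true fall f:

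observed fall = 1 − (1 − f) × (1 + g × d)

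| g | d | g × d | True 12% fall | True 15% fall | True 20% fall |
|---|---|---|---|---|---|
| 5% | 0.20 | 0.010 | 1 − 0.88 × 1.010 = 11.1% | 1 − 0.85 × 1.010 = 14.2% | 1 − 0.80 × 1.010 = 19.2% |
| 8% | 0.40 | 0.032 | 1 − 0.88 × 1.032 = 9.2% | 1 − 0.85 × 1.032 = 12.3% | 1 − 0.80 × 1.032 = 17.4% |
| 12% | 0.60 | 0.072 | 1 − 0.88 × 1.072 = 5.7% | 1 − 0.85 × 1.072 = 8.9% | 1 − 0.80 × 1.072 = 14.2% |

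A fall drops below the 10% line when g × d exceeds 0.90/(1 − f) − 1:

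- For a 12% fall the limit is 0.0227. At g = 8% this needs d above 0.0227/0.08, about 28 points.
- For a 15% fall the limit is 0.0588. At g = 8% no d in the assumed range reaches it (0.08 × 0.60 = 0.048). At d = 0.60 the gain must exceed 9.8%.
- A 20% fall stays above 10% throughout the assumed range.

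The zero reference share matters little. With a share rising from 20% to 60% at g = 8%, a 12% fall is seen as 1 − 0.88 × 1.048/1.016 = 9.2%, as before.

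**One post-rescue reading against a pre-rescue reference.** This is the extreme case (d = 1), with gains up to 20% considered. The gain needed to hide a fall is above 2.3% for a 12% fall, 5.9% for 15%, 12.5% for 20% and 28.6% for 30%. For example, a 20% fall with a 15% gain shows as 1 − 0.80 × 1.15 = 8.0% and is missed. With a 10% gain it shows as 12.0% and is seen. A 30% fall with a 20% gain still shows as 1 − 0.70 × 1.20 = 16%.

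**Errors in the other direction.**

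- No true change, pre-rescue reference, post-rescue reading, 10% gain: a false rise of 10%.
- No true change, post-rescue reference, pre-rescue reading, 12% gain: 1/1.12 − 1, a false fall of 10.7%.
- A true 12% rise while the post-rescue share drops from 40% to zero, at g = 8%: 1.12/1.032 − 1 = 8.5%, so the gain is understated.

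**Can the plan already separate the readings?** In part. For the rescue inhaler, "The eModule records timestamped pre-defined events" (section 2.3.3). Nebuliser and non-digital inhaler use is reported by the patient (sections 5.1, 6.4 and 6.5.1). No section says that spirometer session times are kept, or that the two sources will be linked. The 14-day exclusion around exacerbations in section 9.4.2 applies only to inhalation data in the normative baseline.

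**The case against.** The strongest reply has four parts.

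1. **Source of FEV1.** A reader might infer that home FEV1 is established as the input to both 10% criteria. The documents do not say so. The threshold objective refers to conventional spirometry, the response rule names no source, section 4.2 takes clinical parameters from the EMR, and section 8.1.2.2 abstracts spirometry from the 12 months before biologic initiation. Participants already on a biologic at entry cannot have a pre-biologic FEV1 from the study's home device. This stands. Home FEV1 remains the likely source for within-study change, because section 8.1.2.2 makes it the only study-specific test and the schedule in section 1.3 lists no clinic spirometry. That is inference, not stated text.

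2. **Size.** Every gain and share is assumed, and sections 2.1 and 3 link rescue use to asthma control, not to spirometry times. This stands, so the figures show what could happen and do not estimate what will.

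3. **Unseen material.** The missing restrictions may sit in vendor training, the ATS/ERS criteria or the Manual of Operations. That is possible, but section 8.1.2.5 says that they follow in its own text.

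4. **Remedy.** Restricting the main analysis to pre-rescue sessions would drop data selectively on bad days. At six uses spread evenly over 24 hours, one falls every 4 hours, and few sessions might qualify. The interval in section 6.2.2, "90 mcg, 1 to 2 inhalations every 4 to 6 hours, as needed", is a prescribing interval and not a spirometry washout. This stands, and is why pre-rescue-only belongs in a sensitivity analysis.

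**Conclusion.** The gap is real, and its effect is conditional. As written, the plan neither times home FEV1 against as-needed rescue nor accounts for rescue use in the PIF–FEV1 analysis, so pre- and post-rescue readings can mix in proportions that follow disease state. The falls at risk of being missed are those not far above the 10% line, and at the middle of the assumed range a 15% fall is still seen as 12.3%.

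Two stronger readings are not supported. One is that FEV1 is timed against routine morning or bedtime medication and only rescue is overlooked: that timing is written for PEF, so on a literal reading FEV1 has no medication timing at all. The other is that falls on the worst days will be hidden. Masking needs post-rescue readings compared with a mainly pre-rescue reference, the largest falls remain visible, and the error can run in either direction. This is a worthwhile, inexpensive improvement to the analysis, not a defect that invalidates it.

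**What to change.** 1. Confirm that the home spirometer's session times are kept. In section 9.4.3 item 2, link each FEV1 session to the time since last rescue, using ProAir timestamps plus documented nebuliser and non-digital use.
2. Keep all sessions in the primary PIF–FEV1 and 10% threshold analyses, with time since last rescue as a covariate. Fix in advance its functional form and the coding of sessions with no recent rescue. For change scores, include it for both sessions.
3. Prespecify a pre-rescue-only sensitivity analysis with its cutoff stated and justified. Report how many sessions it drops, and note that it loses bad-day sessions selectively.
4. State which FEV1 source, home or EMR, feeds each 10% criterion.
5. Reconcile the sentence announcing restrictions in section 8.1.2.5 with the rest of that section. No rule on rescue use is proposed here.

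The wording should be settled before the analysis in section 9.4.6, when half the participants have completed six months. The cost is one data-linkage step and some SAP text. The remaining weakness is misclassification where rescue use is self-reported or the patient has stopped using ProAir.

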8.1.2.6 PATIENT REPORTED OUTCOMES

Asthma Control Test (ACT)

The ACT captures asthma symptoms and short acting bronchodilator usage. Questions will be weighted equally and scored per the standardized questionnaire (REF). An ACT score of <19 is consistent with uncontrolled asthma.

Asthma Impairment and Risk Questionnaire (AIRQ)

The AIRQ™ is a patient assessment tool intended to help identify patients 12 years of age and older whose health may be at risk because of uncontrolled asthma. This assessment is based on a series of patient-facing questions about asthma medications, respiratory symptoms, and utilization of health care resources. Depending on the patient's responses to these questions, the patient will receive a score reflecting their level of asthma control.

St. George's Respiratory Questionnaire

The St. George's Respiratory Questionnaire (SGRQ) is a patient reported questionnaire designed to measure impact on overall health, daily life, and perceived well-being in patients with obstructive airways disease. Scores range from 0 to 100 with higher scores indicating more limitations.

8.2 SAFETY AND OTHER ASSESSMENTS

In this study, safety will be assessed by qualified study personnel by evaluating reported adverse events, device safety (as assessed by adverse device effects and serious adverse device effects), and use of concomitant medications.

8.3 ADVERSE EVENTS AND SERIOUS ADVERSE EVENTS

8.3.1 DEFINITION OF ADVERSE EVENTS (AE)

Safety Considerations: The external sponsor/collaborator shall have the sole responsibility for the collection and recording of all reported Adverse Events (AEs), Serious Adverse Events (SAEs), Pregnancies, Adverse Device Effects and Serious Adverse Device Effects throughout the entire study. In keeping with good clinical practice or good pharmacovigilance practice, and 21 C.F.R. Part 314 as the case may be, the external sponsor/collaborator will be required to report and notify the FDA, Institutional Review Boards (IRBs), Teva Pharmaceuticals (Teva), and any other collaborators/investigators of all situations mentioned below, within twenty-four (24) hours from receiving information of the situation. The event will be reported to Teva by submitting the collected information to the Teva Local Safety Officer.

- (a) All related Serious Adverse Events
- (b) All Serious Adverse Device Effects.
- (c) Any medical event which may reasonably be believed to impair the integrity, validity or ongoing viability of the Study

Pharmacovigilance approved definitions of AEs and SAEs and reporting and recording procedures will be followed as noted below.

In this study, safety will be assessed by qualified study personnel by evaluating reported adverse events and device safety (as assessed by adverse device effects and serious adverse device effects). The external sponsor/collaborator will be responsible for the collection and recording of all reported Adverse Events (AEs), Serious Adverse Events (SAEs) Pregnancies, Adverse Device Effects and Serious Adverse Device Effects throughout the entire study.

Definitions:

Adverse Event

An adverse event (AE) is any untoward medical occurrence, unintended disease or injury, or untoward clinical signs (including abnormal laboratory findings) in patients or clinical investigation subjects, users or other persons, whether or not related (causal relationship) to the pharmaceutical product (treatment), investigational medical device, or comparator. This definition includes events related to the procedures involved. For users or other persons, this definition is restricted to events related to investigational medical devices.

An adverse event can, therefore, be any unfavorable and unintended physical sign, symptom, or laboratory parameter that develops or worsens in severity during the course of this study, or significant worsening of the disease under study or of any concurrent disease. A new condition or the worsening of a pre-existing condition will be considered an adverse event. Stable chronic conditions (such as arthritis) that are present before study entry and do not worsen during this study will not be considered adverse events.

Accordingly, an adverse event can include any of the following:

- intercurrent illnesses
- physical injuries
- events possibly related to concomitant medication
- significant worsening (change in nature, severity, or frequency) of the disease under study or other pre-existing conditions
- drug/drug or drug/device or device/device interactions
- events occurring during diagnostic procedures of this study

Worsening of asthma that occurs during the study that is not typical of the patient's daily symptoms or leads to the patient's discontinuation will be considered an adverse event.

8.3.2 ADVERSE DEVICE EFFECT AND REPORTING

An adverse device effect is an adverse event related to the use of an investigational medical device or combination product. This includes adverse events resulting from insufficient or inadequate instructions for use, deployment, implantation, installation, operation, or any malfunction of the investigational

medical device, including any event resulting from user error or from intentional misuse of the investigational medical device.

A serious adverse device effect is an adverse device effect that has resulted in any of the consequences characteristic of a serious adverse event as described in section 8.3.3.

AE=adverse event; ADE=adverse device effect; SADE=serious adverse device effect; SAE=serious adverse event.

